3.2 Primary Endpoints

3.2.1 Primary Safety Endpoint

The primary safety endpoint is freedom from Target Lesion Failure (TLF) at 30 days, defined as a composite of:

- Cardiac death, or
- Myocardial Infarction (per SCAI definition for peri-procedural MI; per 4th Universal Definition for spontaneous MI beyond discharge) attributable to target vessel (TV-MI), or
- Ischemia-driven target lesion revascularization (ID-TLR)

3.2.2 Primary Effectiveness Endpoint

The primary effectiveness endpoint is Procedural Success defined as stent delivery with a residual in-stent stenosis $\leq 30\%$ in all target lesions (core laboratory assessed) and without in-hospital TLF (CEC adjudicated).

3.3 Sample Size Determination

The sample size was calculated based on the precision of the exact 2-sided 95% confidence interval (CI) of the primary effectiveness endpoint, using Disrupt CAD III female subgroup results as a reference [18].

 SHOCKWAVE MEDICAL INC	EMPOWER CAD NCT 05755711
---	-----------------------------

The calculation of the EMPOWER CAD sample size was based on a procedural success estimate of 90.0%. Combined with a desired precision of +/- 3.1% and an alpha of 0.05 (95% CI), a sample size of 360 was selected to provide a probability width (“power”) of 0.8. Assuming a lost-to-follow-up rate of 10%, up to 400 subjects will be enrolled.

The EMPOWER CAD study will enroll a broader population relative to the prior pooled analysis from CAD I-IV; as such, point estimates from this real-world population may be used as reference for future studies.

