	
informed of the nature of the study, agrees to its provisions, and has provided written informed consent, approved by the appropriate Institutional Review Board (IRB) or Ethics Committee (EC)

Study Exclusion Criteria	
1. Subjects with known mental or physical illness or known history of substance abuse that may cause non-compliance with the protocol, confound the data interpretation, or is associated with a life expectancy of less than one year2. Subjects presenting with cardiogenic shock at the time of the index procedure3. Serious angiographic complication in the target vessel prior to treatment with coronary IVL including severe dissection (Type D to F), perforation, abrupt closure, persistent slow-flow or persistent no reflow4. Subject unable to tolerate anticoagulation/antiplatelet therapy per guidelines5. Subject is enrolled in any study of an investigational device or drug that may interfere with study results
Study Statistical Methods	
• Intent-to-Treat (ITT) analysis with pre-defined subgroups• Designed to assess exact 95% confidence interval (CI) for primary endpoints; no formal hypothesis testing
Study Sponsor/Study Management	
Shockwave Medical, Inc. [name] [name] USA
 
Contact: [name] Title: Director, Clinical Affairs Telephone (direct): [contact] Email: [contact]

[REDACTED]	[REDACTED]

EMPOWER CAD

NCT 05755711

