3.0 STATISTICAL CONSIDERATIONS

3.1 General Statistical Methods

Descriptive statistics will be provided in this clinical study. Analyses will be conducted at pre-specified time points including 30 days, 1, 2 and 3 years.

Categorical variables will be summarized by the number of observations available, frequency, and percentage. Unless otherwise noted, missing data will be excluded from the denominator. Comparisons will utilize a Chi-square test, or Fisher's exact test when 20% or more of expected cell frequencies are less than 5. Clinical outcomes analyzed at 30 days will be evaluated as categorical (binary) data. McNemar's chi-square may be used to assess within-subject changes in a bivariate response variable. Exact confidence intervals will be generated for estimates of proportions.

Continuous variables will be summarized by the mean, standard deviation, median, minimum, and maximum. Within-subject changes will be analyzed parametrically using the Paired t-test if the differences are normally distributed, or non-parametrically using the Sign-Rank Test if the differences are not normally distributed. Asymptotic confidence intervals will be generated for estimates of means.

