3.4 Population Analysis

The primary analysis population will be the Intent-to-Treat (ITT) cohort which includes all enrolled subjects.

[figure not shown]

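### Section 3.3: the stated 0.8 probability of an exact 95% CI within +/- 3.1% does not follow from the plan's inputs; read as the chance of that half-width, it is 0.27 with 360 evaluable subjects (0.61 with 400)

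*Combined protocol and SAP*

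**What the plan says.** Section 3.3 (Sample Size Determination) bases the sample size on the "precision of the exact 2-sided 95% confidence interval (CI) of the primary effectiveness endpoint", with procedural success taken as 90.0%. It then gives the target and the result: "desired precision of +/- 3.1% and an alpha of 0.05 (95% CI), a sample size of 360 was selected to provide a probability width", glossed as power, of 0.8. Enrolment follows from that number: "Assuming a lost-to-follow-up rate of 10%, up to 400 subjects will be enrolled".

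Four other places bear on the reading:

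- The Study Summary, under statistical methods: "Designed to assess exact 95% confidence interval (CI) for primary endpoints; no formal hypothesis testing".
- Section 3.2.2 makes the endpoint a residual stenosis result "without in-hospital TLF (CEC adjudicated"), so it is complete at discharge.
- Section 3.4 makes the primary population the "Intent-to-Treat (ITT) cohort which includes all enrolled subjects".
- Section 3.1 says that, unless otherwise noted, "missing data will be excluded from the denominator".

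**The concern.** Every input needed to check the 0.8 is given: interval method, confidence level, assumed rate, half-width and number of subjects. An exact (Clopper-Pearson) interval is wider than the simple normal-approximation (Wald) interval. The Wald formula with no assurance term already needs about 360 subjects for 3.1%. An exact interval with the same n and an 80% assurance therefore cannot be expected to meet 3.1%.

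With no hypothesis test there is no power calculation behind the study, and this statement is all that supports the sample size quantitatively. Section 3.3 also says the estimates may serve as a reference for future studies, so a reader should be able to rely on the stated precision.

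**Working it through.** **Inputs.** All come from section 3.3: true rate p = 0.90, two-sided 95% exact interval, target half-width w = 0.031, n = 360 evaluable and up to 400 enrolled. *Probability width* is undefined and is read here as P(half-width ≤ w).

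**The plan's own figures.** The Wald formula gives n = 1.96² × 0.9 × 0.1 / 0.031² = 359.8, which rounds up to 360. Inflation for 10% loss is 360 / 0.9 = 400, as stated. The 360 thus coincides with a formula that is not exact and contains no 0.8. That the sponsor obtained it this way is an inference.

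**Method for the 0.8.** For each count x from 0 to n, compute the Clopper-Pearson limits L(x) and U(x) and the half-width h(x) = [U(x) − L(x)] / 2. Then sum the Binomial(n, 0.90) probabilities over all x with h(x) ≤ 0.031.

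**At n = 360.**

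- 324/360 (90%): interval 86.4% to 92.9%, h = 3.24%, arms −3.57 and +2.90 points.
- 327/360: h = 3.12%. 328/360 (91.1%): h = 3.08%. At least 328 successes are therefore needed.
- P(X ≥ 328) = 0.274.

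**At other n, true rate 90%.**

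| Evaluable n | Half-width at 90% observed | Mean half-width | Successes needed | P(half-width ≤ 3.1%) |
|---|---|---|---|---|
| 360 | 3.24% | 3.22% | 328 | 0.274 |
| 380 | 3.15% | 3.14% | 344 | 0.407 |
| 400 | 3.06% | 3.05% | 359 | 0.607 |

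The probability is 0.778 at n = 428 and first reaches 0.8 at n = 429 (0.817).

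**Could another reading give 0.8 at n = 360?**

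- Other intervals: Wald 0.544, Jeffreys 0.544, Wilson 0.474, mid-P 0.474, Agresti-Coull 0.405.
- Rounding slack, half-width up to 3.15%, exact interval: 0.337 (0.668 at n = 400).
- Single arms of the exact interval: the upper arm is at most 3.1% with probability 0.834, the lower arm with probability 0.018.
- Higher true rate, exact interval: 0.517 at 91% and 0.768 at 92%; 0.8 is reached only at about 92.2%.

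**What the exact interval does support with probability of at least 0.8, at a true rate of 90%.**

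- n = 360: P(h ≤ 3.42%) = 0.834, against 0.788 for 3.40%.
- n = 400: P(h ≤ 3.22%) = 0.821, against 0.776 for 3.20%.

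**The case against.** The strongest counter-argument is about weight. The study is descriptive, and no success criterion, stopping rule or claim uses the 3.1% or the 0.8. The half-width at 90% observed misses the target by 3.24 − 3.1 = 0.14 percentage points at 360, and meets it at 400. The fall from 0.8 to 0.27 sounds larger than the loss of precision, because the probability moves quickly with small changes in the true rate. This stands, and it limits the point to a correction of the planning text.

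The plan attaches 0.8 to 360 subjects and not to 400. That is also right: the 400 figure is a generous sensitivity check, relevant because an in-hospital endpoint in all enrolled subjects should lose few to follow-up. A Wald or Jeffreys interval does reach 0.821 at 400, but neither is the exact interval the plan names.

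Two other explanations are possible. The exact interval at 360 gives 0.788 for a half-width of 3.4%, so 3.1 may be a slip for 3.4. Or the upper arm alone was used (0.834). The first still leaves a wrong figure in the text. The second contradicts a +/- statement, since the lower arm almost never meets 3.1%.

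Finally, section 1.3 also motivates enrolling up to 400 women as an expansion on the 144 in the pooled analysis. That supports a larger study but gives no precision.

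**Conclusion.** The concern holds. On the natural reading of the term, the probability is 0.27 and not 0.8 at the stated n, rate and interval method, and none of the two-sided half-width readings tried gives more than 0.54 at 3.1%. With all 400 subjects evaluable the half-width target is met at 90% observed, but the probability is 0.61.

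This rests on a true rate of exactly 90%, as the plan states, on the Clopper-Pearson interval as the exact method, and on *probability width* meaning the chance that the half-width is at most 3.1%. The statement should be corrected. The planned analysis and the validity of the reported interval are not affected.

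**What to change.** Keep the sample size and replace the precision statement in section 3.3 with wording to this effect:

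- With 360 evaluable subjects and 90% observed success, the exact 95% CI is 86.4% to 92.9% (half-width 3.24%; arms −3.57 and +2.90 points). At a true rate of 90%, the half-width will be at most 3.42% with probability of at least 0.8.
- With 400 evaluable subjects and 90% observed success, the exact 95% CI is 86.6% to 92.8% (half-width 3.06%). At a true rate of 90%, the half-width will be at most 3.22% with probability of at least 0.8.

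If *probability width* was meant in another sense, define it and name the interval method behind the calculation.

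The cost is a change of wording in one section. Enrolment, endpoints and analyses stay as they are; the stated precision at 360 becomes slightly less favourable.

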3.4 Population Analysis

The primary analysis population will be the Intent-to-Treat (ITT) cohort which includes all enrolled subjects.

[figure not shown]
3.5 Handling of Dropout of Missing Data

No imputation of or adjustments for missing data will be performed for the primary analyses. All available data will be presented. For time to event analyses, subjects who do not experience the event in question will be censored at their last known follow-up.

EMPOWER CAD

NCT 05755711

EMPOWER CAD

NCT 05755711

5.0 Index Procedure

5.1 Coronary Intravascular Lithotripsy Procedure

A full description of the IVL procedure is detailed in the Instructions for Use (IFU) including appropriate balloon sizing. Note that there are specific IFUs and labelling provided for the United States (US) and for Outside of the US (OUS). An appropriately-sized IVL catheter should be selected per the IFU.

The recommended procedural steps outlined below represent an “IVL first” approach; adjunctive devices may be used if there are challenges after first attempting to cross with the IVL catheter [REDACTED]

[REDACTED] Any departures from this algorithm will not be considered protocol deviations; information on all devices used in the procedure (including the order in which they were used) will be captured. Angiographic images captured during the procedure will be sent to the core lab for analysis.

- If multiple lesions are to be treated, it is recommended that non-target lesions be preferentially treated first.
- If a serious angiographic complication occurs in a target or non-target vessel prior to insertion of the IVL catheter, the subject should be treated per standard of care; however, they should not be enrolled in the study.
- If the Investigator is able to pass a guidewire but is unable to pass the IVL catheter across the target lesion, an adjunctive tool (balloon, atherectomy, cutting/scoring balloon) may be used prior to re-insertion of the IVL Catheter. The lesion will then be treated per the IFU with the IVL Catheter.

Note: Pre-dilatation may be performed using standard techniques based on physician discretion.

- The subject is considered enrolled once the IVL Catheter has been inserted into the access artery.
- Once the IVL catheter is placed in the target lesion area, the balloon should be inflated to 4 atm and IVL treatment delivered for the pre-programmed time of 10 seconds to deliver 10 pulses.

Note: The IVL Generator is programmed to force a minimum pause time of 10 seconds following every 10 pulses delivered.

- Following IVL, inflate the balloon to the reference size using the balloon compliance chart (refer to IFU) and record lesion response on fluoroscopy.
- Deflate the balloon to re-establish blood flow.
- Repeat prior steps for additional treatment cycles until the lesion has been sufficiently dilated or the catheter is re-positioned.

If additional lesion area needs to be treated, follow the treatment steps identified above and per the IFU to ensure appropriate overlap between segments [REDACTED]

[figure not shown]
Note: The maximum number of pulses to treat a single arterial segment is 80 pulses and therefore 160 pulses in an overlap segment. Additional catheters may be used when necessary.

EMPOWER CAD

NCT 05755711

- The residual stenosis will be assessed by the physician following the IVL procedure. The IVL procedure is considered successful when the residual stenosis allows for adequate balloon expansion by visual estimate, as determined by the Investigator prior to stent placement. Consider additional IVL pulses if needed to optimize residual stenosis.
- If the residual stenosis is sub-optimal following IVL, a balloon or other adjunctive device (atherectomy, cutting/scoring balloon) must be used to dilate the lesion prior to stenting. This information will be recorded in the case report form.
- Post-IVL angiography should be performed after IVL pulses have been delivered and prior to stent delivery.
- The stent will then be delivered using a standard approach.
- Following stent implantation, post-dilatation with a non-compliant balloon with inflation pressure ≥ 16 atm is strongly recommended.
- Following delivery of the coronary stent and post-dilatation, angiography will be performed to determine the final residual stenosis for assessment of the primary effectiveness endpoint.

5.2 Optical Coherence Tomography (OCT) Sub-study

For subjects enrolled in the OCT Sub-study, OCT images must be assessed at baseline, immediately post-IVL (or post-adjunctive therapy), and end of procedure.

